11.8 Appendix 8. Protocol-specific Anticipated Serious Adverse Events

Anticipated serious adverse events are events that are anticipated to occur in the study population at some frequency independent of investigational product exposure and do not need to be reported individually as an FDA IND safety report by the sponsor.

Identification and reporting of anticipated serious adverse events is the responsibility of the sponsor; the investigator is responsible for reporting adverse events and serious adverse events as described in Section 11.4.

Anticipated Serious Adverse Events for Study 20180292

Weight decreased
Decreased appetite
Fatigue
Anaemia
Gastric obstruction
Helicobacter infection
Pernicious anaemia
Barrett's oesophagus
Dyspepsia
Gastrooesophageal reflux disease
Nausea
Vomiting
Abdominal pain
Gastritis
Gastric hemorrhage
Gastric perforation

For metastatic site-related adverse events, events will be evaluated for ASAEs on a case by case basis (eg, intestinal obstruction for intestinal metastatic disease state, increase in transaminase for liver metastatic disease present at baseline).

11.9 Appendix 9. Operating Characteristic for 2-parameter BLRM Design

The operating characteristics of the 2-parameter Bayesian logistic regression model (BLRM) design were evaluated via simulation using EAST software version 6.4.1. A bi-variate normal prior distribution (parameters “a” and “b”) is used for the BLM model. The prior distribution is specified such that probability of dose-limiting toxicity (DLT) is 0.05 for the starting dose (6.5 µg) and 0.3 for the reference dose (3500 µg), where the probability that the true DLT rate is ≤ 0.40 at the lowest planned dose is 0.90 and the probability the true DLT rate is ≤ 0.05 at the reference dose is 0.05. In particular, the parameters of the bi-variate normal prior are as follows: the mean natural log (ln) of “a” ln(a) = -0.847, standard deviation (SD) of “a” SD(a) = 1.275, mean ln(b) = -1.098, SD(b) = 1.981 and correlation = 0.

The planned cohort size for the initial 2 cohorts is n=1 subject and the cohort size for subsequent cohorts is fixed to 3 or 4 subjects; based on observed toxicity in the initial 2 cohorts, the cohort size for any or all of the initial 2 cohorts may be increased to n = 3 to 4 subjects. Planned dose levels are 6.5, 20, 65, 200, 400, 650, 1000, 1500, 2300 and 3500 µg. After simulated enrollment of the initial cohort at the initial dose level, simulations selected the subsequent dose levels based on the following rules:

- After each cohort, the next dose was the 1 with the highest probability of the target toxicity probability interval (TPI), but with a less than 0.40 probability of an excessive or unacceptable TPI.
- Skipping a planned dose level was not allowed.

Dose exploration was stopped when either of the following occurred:

- The model recommended a dose level where at least 6 subjects had already received treatment at this recommended level.
- A maximum number of 34 subjects were treated.

Operating characteristics are described below.

Operating characteristics

The design was evaluated for 4 possible dose-response scenarios: “Low”, “Mid”, and “High” maximum tolerated dose (MTD) and an “Extreme” scenario where every planned dose level was excessively toxic. [Table 11-4](#) shows the dose level and true probability of dose-limiting toxicity (DLT) for each scenario used in the simulated studies. Since the timing of initiation of the multiple subject cohorts impacts the design operating characteristics, the operating characteristics were calculated separately for each possible timing for starting the multiple subject cohorts: at cohort 1, cohort 2 and at

cohort 3. Overall operating characteristics are reported after weighting the 3 timing-specific operating characteristics by the probability that a specific cohort is the initial multiple subject cohort. [Table 11-5](#) shows the dose level and true probability of a DLT or a grade 2 related adverse event for each scenario used in the simulated studies. Using the toxicity rates described in [Table 11-5](#), the probability by cohort for initiating the multiple subject cohorts are shown in [Table 11-6](#). [Table 11-7](#) reports the operating characteristics from 1000 simulated studies estimating the MTD when the target TPI is (0.20, 0.33]. The rate of MTD selected and the average number of subjects assigned to each dose level are presented in [Table 11-8](#).

Table 11-4. True Probability of DLT by Scenario

Dose level (µg)	6.5	20	65	200	400	650	1000	1500	2300	3500
MTD scenario										
High	0.01	0.04	0.08	0.10	0.12	0.15	0.20	0.30	0.40	0.50
Mid	0.08	0.10	0.12	0.15	0.20	0.30	0.40	0.50	0.60	0.70
Low	0.12	0.15	0.20	0.30	0.40	0.50	0.60	0.70	0.80	0.90
Extreme	0.35	0.40	0.45	0.55	0.60	0.65	0.70	0.75	0.80	0.95

DLT = dose-limiting toxicity; MTD = maximum tolerated dose

Table 11-5. True Probability of DLT or Grade 2 Related Adverse Event by Scenario

Dose level (µg)	6.5	20	65	200	400	650	1000	1500	2300	3500
MTD scenario										
High	0.06	0.09	0.13	0.15	0.17	0.25	0.30	0.40	0.50	0.60
Mid	0.13	0.15	0.17	0.25	0.30	0.40	0.50	0.60	0.70	0.80
Low	0.17	0.25	0.30	0.40	0.50	0.60	0.70	0.80	0.90	0.95
Extreme	0.45	0.50	0.55	0.65	0.70	0.75	0.80	0.85	0.90	0.99

DLT = dose-limiting toxicity; MTD = maximum tolerated dose

Table 11-6. Probability by Planned Dose Level for Initiating Multiple Subject Cohorts by Scenario

Dose level (µg) for initiating multiple subject cohorts	6.5	20	65
MTD scenario			
High	0.06	0.08	0.86
Mid	0.13	0.13	0.74
Low	0.17	0.21	0.62
Extreme	0.45	0.27	0.27

Table 11-7. Operating Characteristics by Scenario

MTD scenario	High	Mid	Low	Extreme
Number of subjects per cohort	4	3	4	3
Average number of subjects on study	30.1	25.2	26.2	20.8
Average number of DLTs on study	5.2	4.8	5.9	5.0
Percentage of studies by actual DLT probability of estimated MTD:				
MTD below lowest planned dose	3.1	1.7	6.4	6.2
DLT probability at estimated MTD				
< 10%	1.3	2.1	0.1	0.2
≥ 10% and < 20%	17.6	18.5	17.3	19.4
≥ 20% and < 33%	56.1	54	51.4	46.5
≥ 33%	18.3	19	24.7	27.7
≥ 15% and ≤ 33%	66.2	64.6	63.4	58.7

DLT = dose-limiting toxicity; MTD = maximum tolerated dose

Table 11-8. The Rate of MTD Selected and the Number of Subjects Assigned at Each Dose Level by Scenario

MTD scenario	High		Mid		Low		Extreme	
Number of subjects per cohort	4	3	4	3	4	3	4	3
Rate of MTD selected at each dose level (%):								
Below lowest dose	3.1	1.7	6.4	6.2	19.8	16.7	79.9	68.8
6.5 µg	0	0	0.1	0.2	0.8	1.5	4.7	8.4
20 µg	0	0.1	0.6	1.1	4.4	4.2	6.7	8.6
65 µg	1.3	2	4.7	6.1	22.4	21.6	6	9.5
200 µg	2.8	3.4	12	12.2	30.5	27.9	1.5	3.1
400 µg	4.7	4.5	22.8	19.7	16.5	20	0.2	0.4
650 µg	10.1	10.6	28.6	26.8	4.8	6.9	0	0.1
1000 µg	23.7	22.3	18.6	18.7	0.6	1.3	0	0
1500 µg	32.4	31.7	5.6	8	0.1	0.1	0	0
2300 µg	18.3	19	0.5	1	0	0	0	0
3500 µg	3.7	4.7	0	0.1	0	0	0	0
Average number of subjects at each dose level								
6.5 µg	0.2	0.2	0.7	0.5	1.2	1	2.8	2.2
20 µg	0.7	0.6	1.3	1.1	2.5	1.9	2.9	2.4
65 µg	4.4	3.4	4.7	3.6	5.5	4.2	2.6	2.3
200 µg	4.5	3.4	5	3.6	5.1	3.9	0.8	0.9
400 µg	4.5	3.4	5.2	3.8	3.4	2.9	0.2	0.2
650 µg	4.7	3.6	4.8	3.7	1.4	1.6	0	0.1
1000 µg	4.8	3.8	3.2	2.8	0.4	0.5	0	0
1500 µg	4.1	3.7	1.1	1.3	0	0.1	0	0
2300 µg	1.9	2.4	0.2	0.4	0	0	0	0
3500 µg	0.3	0.7	0	0	0	0	0	0

MTD = maximum tolerated dose

11.10 Appendix 10. Performance Status According to Eastern Cooperative Oncology Group (ECOG) Scale

ECOG Performance Status Scale	
Grade	Descriptions
0	Fully active, able to carry on all pre-disease performance without restriction
1	Restricted in physically strenuous activity but ambulatory and able to carry out work of a light or sedentary nature, eg, light house work, office work
2	Ambulatory and capable of all selfcare but unable to carry out any work activities. Up and about more than 50% of waking hours
3	Capable of only limited selfcare, confined to bed or chair more than 50% of waking hours
4	Completely disabled. Cannot carry on any selfcare. Totally confined to bed or chair
5	Dead

ECOG = Eastern Cooperative Oncology Group.

Source: Oken, et al., 1982

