- Subjects who discontinue from the study prior to completing the DLT assessment window for reasons other than a DLT will be considered non-evaluable for dose-escalation decisions and MTD determination and may be replaced by an additional subject at that same dose level.

Dose Level Determination

A recommendation to escalate to a higher dose level will only occur when the previous dose level has been found to be reasonably tolerated based on available study data and upon unanimous agreement of the DLRT members. Available data from previous cohorts will also be considered. Dose level recommendations will be made on a treatment cohort basis (not on an individual basis). After receiving the DLRT recommendation, Amgen will issue a written notification of the dose change decision to investigators. Further information on dose level review meetings is provided in Appendix 3 (Section 11.3).

Dose Cohort Stopping Rules

Dose escalation will follow the pre-defined dose levels in [Table 6-2](#) until a subject experiences a DLT. Then the dose for the subsequent cohorts will be decided by the DLRT after evaluating all available safety, laboratory, and PK data as well as the recommendation from the BLRM. Dose escalation/de-escalation decisions in multiple-subject cohorts will be guided by the BLRM model of dose toxicity. The MTD for BLRM is the dose level predicted to have the highest probability of a DLT rate within the target interval of 20% to 33%, subject to overdose control. To control the risk of overdose, the MTD must have less than a 40% predicted probability of overdosing (DLT rate > 33%).

If late onset adverse events (ie, after the 28-day DLT period) occur or late findings from endoscopic evaluations are reported during a cohort, the DLRT may adaptively re-consider the doses evaluated within a cohort for subsequent dosing and/or possibly trigger a de-escalation or withholding of additional doses in subsequent cohorts. Based on the BLRM model and after reviewing all available safety and tolerability data, the DLRT may recommend dosing at intermediate dose levels between the planned dose levels in [Table 6-2](#).

The Amgen Medical Monitor may suspend dosing and convene a dose level review meeting (DLRM) at any time based on emerging safety data.

Dose escalations will end once any of the following events occur:

- Highest planned dose level is determined to be safe and tolerable (minimum of 6 treated subjects on this dose level).

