- The MTD is identified. A dose level is considered the MTD when the BLRM recommends treatment at this dose level and 6 or more evaluable subjects have already been treated at this dose level.

- On the basis of a review of real-time safety data and available preliminary PK data, dose escalation may be halted or modified by the Sponsor as deemed appropriate. A re-evaluation of the risk/benefit for the study will be necessary after the following observations:
 - Gastrointestinal events of CTCAE grade 3 in 2 subjects, with the exemption of nausea, vomiting, and abdominal pain, and gastrointestinal events of CTCAE grade 4 in 2 subjects if events are at least possibly related to AMG 910
 - Gastrointestinal event of CTCAE grade 5 in 1 subject, at least possibly related to AMG 910

To acquire additional safety and pharmacodynamic data to better inform the RP2D, additional subjects may be enrolled at a dose level that has been shown to not exceed the MTD based on the dose-escalation criteria described above, and at which there is evidence of anti-tumor activity and/or pharmacodynamic biomarker modulation. Up to approximately 3 additional subjects per dose level may be enrolled.

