9.6 Safety Analyses

9.6.1 Analyses of Primary Safety Endpoints

Unless otherwise specified, statistical analyses on safety endpoints will be done using subjects from the Safety Analysis Set, which includes subjects that are enrolled and received at least 1 dose of AMG 910.

The analysis of DLTs will be conducted on the DLT Analysis Set. The probability of a subject having a DLT by planned dose level will be estimated using a two-parameter BLRM model.

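### On the current dose ladder, with clean lower cohorts, the Appendix 9 prior keeps the 40% overdose limit from binding after 2/4 or 3/6 DLTs at 60 µg, and lets 4/6 or more count as the MTD

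*Protocol*

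**What the plan says.** Protocol Section 6.2.1.1.2 has the two-parameter Bayesian logistic regression model (BLRM) guide dose decisions. The target is a DLT rate of 20% to 33%. "To control the risk of overdose, the MTD must have less than a 40% predicted probability of overdosing (DLT rate > 33"%). The same section defines the endpoint of escalation: "A dose level is considered the MTD when the BLRM recommends treatment at this dose level and 6 or more evaluable subjects" have been treated there. The final MTD is a BLRM estimate from all data (Protocol 6.2.1.2; SAP Section 5), and SAP 9.6.1 adds: "The probability of a subject having a DLT by planned dose level will be estimated using a two-parameter BLRM model".

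The prior appears only in Protocol Appendix 9. It is set so that the "probability of dose-limiting toxicity (DLT) is 0.05 for the starting dose (6.5 µg) and 0.3 for the reference dose (3500 µg"), and it further requires that "the probability that the true DLT rate is ≤ 0.40 at the lowest planned dose is 0.90" and that "the probability the true DLT rate is ≤ 0.05 at the reference dose is 0.05". The mean of ln(a) is -0.847, and the rest is "SD(a) = 1.275, mean ln(b) = -1.098, SD(b) = 1.981 and correlation = 0". I read the SDs as those of ln(a) and ln(b), because that reading reproduces the stated tail probabilities.

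Appendix 9 simulates this prior on a ladder of 6.5 to 3500 µg. Table 6-2 now runs 6.5, 15, 30, 60, 150, 300, 600, 1000, 2000 µg. No prior or simulation is given for that ladder.

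**The concern.** The overdose limit exists to stop the model when the data point to a DLT rate above 33%. Half the subjects having a DLT at a dose is such a signal. If the limit stays slack there, the quantitative ceiling on the DLRT does not protect. The MTD definition is a second exposure, because it rests on the BLRM recommendation and the number treated; the DLRT vote does not appear in it. The reported DLT probabilities are a third.

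The plan's simulations could not have shown this. In Table 11-4 neighbouring doses never differ by more than 0.10 in true DLT rate (0.15 in the Extreme scenario), so no steep curve was tried. Protocol 4.1 reports cytokine release events in cohort 1 that forced a change of dosing, so a steep curve is a reasonable case to examine.

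**Working it through.** **Model and rule.** logit p(d) = ln(a) + b·ln(d/3500), with ln(a) ~ N(-0.847, SD 1.275) and ln(b) ~ N(-1.098, SD 1.981), independent. Choose the dose with the largest P(0.20 < p ≤ 0.33) among those with P(p > 0.33) < 0.40, at most one level up (Appendix 9, Section 6.2.1.1.2). Posteriors are by two-dimensional grid integration. Assumptions: this prior carries over to Table 6-2, and the Table 6-2 target dose is the dose in the model.

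**The plan's own figures first.** At 3500 µg, 1/(1 + e^0.847) = 0.300. At 6.5 µg, ln(6.5/3500) = -6.289 and e^-1.098 = 0.3335, so the logit is -0.847 - 2.097 = -2.944, which gives 0.050. P(rate ≤ 0.05 at 3500) = Φ((-2.944 + 0.847)/1.275) = Φ(-1.645) = 0.050. P(rate ≤ 0.40 at 6.5) = 0.896. Re-simulating Appendix 9 on its own ladder (cohorts of 4, 500 trials) selects below the lowest dose in 3.6% (High), 19.4% (Low) and 84.0% (Extreme), against 3.1%, 19.8% and 79.9% in Table 11-8. Mid matches less well (10.6% against 6.4%).

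**60 µg on the current ladder.** The first column gives subjects, all without DLT, at 6.5/15/30 µg.

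| Lower doses | DLTs at 60 | Mean at 60 | P(>33%) at 60 | P(target) 60 vs 150 | P(>33%) at 150 | Model's dose |
|---|---|---|---|---|---|---|
| 3/3/3 | 2/4 | 0.17 | 0.066 | 0.267 vs 0.328 | 0.126 | 150 |
| 3/3/3 | 3/6 | 0.21 | 0.116 | 0.376 vs 0.412 | 0.208 | 150 |
| 4/4/4 | 2/4 | 0.15 | 0.031 | 0.205 vs 0.284 | 0.080 | 150 |
| 4/4/4 | 3/6 | 0.18 | 0.061 | 0.318 vs 0.388 | 0.142 | 150 |
| 6/3/3 | 2/4 | 0.15 | 0.034 | 0.212 vs 0.291 | 0.088 | 150 |
| 6/3/3 | 3/6 | 0.19 | 0.066 | 0.326 vs 0.391 | 0.155 | 150 |
| 1/1/3 | 3/6 | 0.26 | 0.261 | 0.404 vs 0.399 | 0.353 | 60 |

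For contrast, a flat Beta(1,1) prior on the 60 µg data alone gives P(>33%) = 0.80 for 2/4 and 0.83 for 3/6.

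**MTD definition.** Take 0/6 at 6.5 µg and 0/3 at each level between.
- 4/6 at 60 µg: P(>33%) 0.17, posterior mean 0.24, held at 60.
- 4/6 at 150 µg: 0.19, mean 0.24, held at 150.
- 5/6 at 150 µg: 0.36, mean 0.30, held at 150.

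Each has six subjects at the recommended dose, so each is the MTD as defined.

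**Why.** Suppose the true rate is 0.05 at 6.5 µg and 0.50 at 60 µg. Since ln(60/3500) = -4.066, b = 2.944/(6.289 - 4.066) = 1.325 and ln(a) = 1.325 × 4.066 = 5.39. That slope is only (0.281 + 1.098)/1.981 = 0.7 prior SD from its mean, but ln(a) is (5.39 + 0.847)/1.275 = 4.9 SDs out. The prior almost rules such a curve out. With reference 600 µg, mean -0.85 and SD 2, the same curve needs ln(a) = 1.325 × 2.303 = 3.05, which is (3.05 + 0.85)/2 = 1.95 SDs.

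**Which part of the prior is responsible.**
- Reference 2000 or 1000 µg, recalibrated to 0.05 and 0.30, SDs unchanged: still 150 µg after 2/4 and 3/6.
- Reference 300 µg on the same terms: 3/6 holds, 2/4 still gives 150.
- Reference 3500 µg with SD of ln(a) 2 and ln(b) ~ N(0,1): 2/4 still gives 150; 3/6 holds for 6/3/3 and 3/3/3 but not 4/4/4.
- Reference 150 µg alone: neither result escalates.
- Reference 600 µg, SD 2, ln(b) ~ N(0,1): both results hold at 60 in all four lower-dose histories.

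**Trial level.** With true DLT rates .02/.02/.05/.25/.55/.75/.85/.90/.95 over the nine doses, cohorts of 3, a cap of 34 and no DLRT, the plan's prior selects a dose with true rate above 33% in 43% to 51% of 1000 trials, depending on how the first cohort is handled. The 600 µg prior gives about 21%.

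**The case against.** Escalation is not automatic. The BLRM recommendation is a ceiling, the previous dose must be reasonably tolerated, and the DLRT must agree unanimously (Protocol 6.2.1.1.2, Appendix 3). A one-parameter CRM may be run as a sensitivity check (9.4.1.1), and expansion has its own toxicity boundary. All of this stands, so the simulated rates above describe the model without its clinical gate.

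The cells also depend on history. 3/6 holds at 60 µg after 1, 1 and 3 clean subjects, or after one DLT at 30 µg. 3/3 at 60 µg holds if 6.5 µg has 0/3 rather than 0/6. 5/6 at 60 µg after 0/6, 0/3, 0/3 de-escalates to 30. 5/6 at 150 µg drops to 60 if every lower level has 0/3. By contrast, 2/4 at 60 µg gave 150 in every lower-dose history tested.

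Pooling clean lower cohorts is what a dose-response model is for, and how hard to lean against overdosing is a calibration judgement. Table 11-8 already discloses overdose selection of about 22% to 28% in the Low scenario. Replacing the prior now, with the study closing, would be post hoc. That argues for a sensitivity run rather than substitution.

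A reader might infer that the 3500 µg reference by itself defeats the overdose control, or that the trial would have escalated on these data. The documents do not support either. Moving the anchor to 2000 or 1000 µg changes nothing, the 40% limit operates as written but stays slack, and the DLRT could refuse.

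**Conclusion.** The point holds for the model's output, conditional on clean lower cohorts of 3 to 4 subjects and on the Appendix 9 prior being the one in use. After 50% observed DLTs at 60 µg the model puts the chance of exceeding 33% at 0.03 to 0.12 and prefers 150 µg. With 0/6 at 6.5 µg and 0/3 at each level between, it can also label 4/6 at 60 µg, or 4/6 to 5/6 at 150 µg, as the MTD for a 20% to 33% target. The cause is the combination of a distant anchor, a tight ln(a) prior and the slope prior. The DLRT limits the effect on actual escalation. It does not enter the MTD definition, and it does not correct the shrinkage in the SAP 9.6.1 probabilities.

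**What to change.** 1. On the Table 6-2 ladder, print the decision table: the model's recommendation for each number of DLTs out of 3, 4 and 6 at each level, with the lower-dose data assumed.
2. Re-run the operating characteristics on that ladder with at least one steep curve.
3. Recalibrate the reference dose, the SD of ln(a) and the slope prior together. Moving the reference inside the ladder is not enough. The model should neither escalate after about 50% observed DLTs nor name a dose with 4/6 or more as the MTD, and it should not stall after 1/6. The last check matters: with reference 150 µg, SD 2 and ln(b) ~ N(0,1), the model is at the 40% limit after 1/6 at 60 µg and holds after 1/6 at 150 µg. The 600 µg example passes all three checks at 60 and 150 µg; other levels were not checked for it.
4. SAP 7.1 says the study is ending early. For SAP 9.6.1, keep the original prior as the planned estimate, add the recalibrated prior as a labelled sensitivity run, and show both beside the observed DLT counts by dose.

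The cost is software time and new text, with no extra subjects. The statistical price is lower target selection when the curve is shallow and the MTD is high. In one such scenario it fell from 86% to 40% with the 600 µg prior. A run with true rates .01/.02/.03/.05/.07/.10/.15/.20/.30 gave 87% and 41%. That trade-off should be stated beside the chosen prior.

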6.2 Dose Modification

6.2.1 Dose-cohort Study Escalation/De-escalation and Stopping Rules

6.2.1.1 Dose-exploration Phase

The dose-exploration phase of the study will enroll up to 34 subjects with gastric cancer.

[Table 6-2](#) describes the planned dose levels for investigation. Dose exploration will be conducted in 2 stages: single-subject cohort(s) followed by multiple-subject cohort(s) (3 to 4 subjects per cohort).

Table 6-2. Planned AMG 910 Target Doses per Dose Cohort Level

Cohort number	Number of subjects ^a	Dose (µg) Route
(-1)	(3 to 4)	2.5 IV
1	3 to 4	6.5 ^b eIV
1b	3 to 4	6.5 ^b eIV
2b	3 to 4	15 eIV
3b	3 to 4	30 eIV
4b	3 to 4	60 eIV
5b	3 to 4	150 eIV
6b	3 to 4	300 eIV
7b	3 to 4	600 eIV
8b	3 to 4	1000 eIV
9b	3 to 4	2000 eIV

Routes of administration: eIV = **extended intravenous**; IV = **short-term** intravenous.

^a Switching from a single subject cohort to a multiple-subject cohort will occur with cohort 3 or sooner if specific safety criteria are observed as described in Section [6.2.1.1.1](#).

^b If a dose reduction is needed according to instructions provided in [Table 6-3](#), treatment will be continued at a dose of 2.5 µg as specified in Section [6.2.2.3.5](#).

Note: The “b” cohort numbers are used to differentiate cohorts 1 through 10 denoted in previous versions of the protocol.

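### Appendix 9's BLRM operating characteristics belong to a superseded dose grid; its tables also understate over-toxic MTD selection in the High scenario and leave the single-subject cohorts out of the subject counts

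*Protocol*

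**What the plan says.** Appendix 9 (protocol 11.9) describes the simulated design: "Planned dose levels are 6.5, 20, 65, 200, 400, 650, 1000, 1500, 2300 and 3500" µg, and "The planned cohort size for the initial 2 cohorts is n=1 subject", with 3 or 4 per cohort afterwards and a cap of 34. Table 11-4 gives the true DLT rate per dose and scenario. Table 11-6, "Probability by Planned Dose Level for Initiating Multiple Subject Cohorts by Scenario", supplies the weights used to combine the three possible start points of the multiple-subject stage. Table 11-7 reports "Percentage of studies by actual DLT probability of estimated MTD" and "Average number of subjects on study". Table 11-8 gives the selection rate and "Average number of subjects at each dose level".

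Table 6-2 (protocol 6.2.1.1) lists 6.5, 15, 30, 60, 150, 300, 600, 1000 and 2000 µg, plus a level −1 at 2.5 µg, with 3 to 4 subjects in every row. SAP 3.1.1 and SAP Table 3-1 give the same doses. The note to Table 6-2 explains that the b-suffixed "cohort numbers are used to differentiate cohorts 1 through 10 denoted in previous versions of the protocol". Footnote a to the same table still says "Switching from a single subject cohort to a multiple-subject cohort will occur with cohort 3 or sooner", and protocol 6.2.1.1.1 and SAP 3.1.1 still pre-plan two single-subject cohorts.

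**The concern.** Appendix 9 is current text, and it calls planned a set of doses that the current plan does not use. Its ten levels match the ten cohorts that the Table 6-2 note assigns to previous versions, so it appears not to have been updated when the grid changed. A reader who wants to know how often the present design picks an over-toxic or a too-low dose cannot learn it there.

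The tables also disagree with each other. Table 11-7 should be a regrouping of Table 11-8, but its High columns do not add to 100%, and the shortfall lies in the over-toxic band, which makes the design look safer than simulated. A mean below one subject at the starting dose is impossible if everyone treated is counted.

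The SAP still estimates DLT probabilities and the final MTD with the two-parameter BLRM (SAP 5 and 9.6.1). It states no prior, so Appendix 9 also holds the only description of the model's prior.

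**Working it through.** **Grid.** Comparing {6.5, 20, 65, 200, 400, 650, 1000, 1500, 2300, 3500} with {6.5, 15, 30, 60, 150, 300, 600, 1000, 2000}, the common levels are 6.5 and 1000 µg: two of the nine current levels.

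**Which columns of Table 11-7 can be read.** Four value columns survive in the text. They are High at 4 and 3 per cohort and Mid at 4 and 3, because the below-lowest-dose rates (3.1, 1.7, 6.4, 6.2) and the average trial sizes match those columns of Table 11-8. The Low and Extreme cells of Table 11-7 are not legible, and nothing is claimed about them.

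**Selection bands.** I grouped the Table 11-8 selection rates by the Table 11-4 true DLT rates.

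| Band, High scenario | Doses (µg) | 4 per cohort: regrouped / printed | 3 per cohort: regrouped / printed |
|---|---|---|---|
| <10% | 6.5–65 | 1.3 / 1.3 | 2.1 / 2.1 |
| 10 to <20% | 200–650 | 2.8+4.7+10.1 = 17.6 / 17.6 | 3.4+4.5+10.6 = 18.5 / 18.5 |
| 20 to <33% | 1000, 1500 | 23.7+32.4 = 56.1 / 56.1 | 22.3+31.7 = 54.0 / 54 |
| ≥33% | 2300, 3500 | 18.3+3.7 = **22.0** / 18.3 | 19+4.7 = **23.7** / 19 |
| 15 to 33% | 650–1500 | 66.2 / 66.2 | 64.6 / 64.6 |

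Only the ≥33% row fails, and its printed values equal the 2300 µg row alone. Including the below-lowest-dose rate, the printed columns total:

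- 4 per cohort: 3.1+1.3+17.6+56.1+18.3 = 96.4
- 3 per cohort: 1.7+2.1+18.5+54+19 = 95.3

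With 22.0 and 23.7 they total 100.1 and 100.0. The Mid cells all reproduce to within 0.1 (for ≥33%: 18.6+5.6+0.5 = 24.7 as printed; 18.7+8+1+0.1 = 27.8 against 27.7), and the printed Mid columns total 99.9 and 100.0.

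**Subject counts.** The Table 11-8 means per dose add exactly to the Table 11-7 averages: 30.1 and 25.2 (High), 26.2 and 20.8 (Mid). Let p1 be the Table 11-6 probability that multiple-subject enrollment starts at 6.5 µg, and m the cohort size. The smallest possible mean at 6.5 µg is m·p1 + (1 − p1)·1.

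| Scenario | p1 | Minimum, m = 4 | Printed | Minimum, m = 3 | Printed |
|---|---|---|---|---|---|
| High | 0.06 | 0.24+0.94 = 1.18 | 0.2 | 0.18+0.94 = 1.12 | 0.2 |
| Mid | 0.13 | 0.52+0.87 = 1.39 | 0.7 | 0.39+0.87 = 1.26 | 0.5 |
| Low | 0.17 | 0.68+0.83 = 1.51 | 1.2 | 0.51+0.83 = 1.34 | 1 |

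The printed High values match m·p1 alone (0.24, 0.18), which is what remains if single subjects are dropped. The 6.5 µg row is short by at least 0.98 and 0.92 in High and 0.69 and 0.76 in Mid. In Extreme the bound (2.35, 1.9) is not violated by the printed 2.8 and 2.2, so it shows nothing there.

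The expected number of omitted singles, counting a single who triggers the switch within the enlarged cohort, is:

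- High: 0.08×1 + 0.86×2 = 1.80
- Mid: 0.13×1 + 0.74×2 = 1.61

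As support only, an independent simulation of the Appendix 9 rules (600 runs per start timing) with the singles counted and modelled gave average sizes of 31.3 and 27.0 (High) and 27.5 and 22.7 (Mid), which is 1.2, 1.8, 1.3 and 1.9 above print. The High below-lowest-dose rate was 3.4% and 1.9% without the singles but 0.3% and 0.1% with them, against 3.1% and 1.7% printed. The singles may therefore be missing from the model data as well as from the counts.

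**The case against.** - **Cohort size is not contradicted.** Appendix 9 goes on to allow either of the first two cohorts to be enlarged to 3 or 4 and simulates a multiple-subject start at cohort 1, and protocol 4.1 reports CRS events in cohort 1. This stands as a reading of the rule. The reported results, however, give weight 0.86 (High) and 0.74 (Mid) to trials with two single-subject cohorts, so they do not describe a plan with 3 to 4 in every row.
- **Other evidence exists, and sample size does not rest on Appendix 9.** Protocol 9.2 gives the chance of at least one DLT per cohort and bases the escalation size on practical grounds. The second half stands. The first does not: those are binomial probabilities for one cohort and say nothing about how the escalation selects a dose.
- **The grid point has no measured effect, and intermediate doses are allowed.** It is true that no change in performance on the current grid is quantified here. That is a reason to accept a label in place of a re-run, but not to leave the old grid described as planned.
- **The undercount in the totals is not exactly known.** This stands. The impossibility at 6.5 µg is proven; the size of the correction is approximate.
- **Little turns on it.** Table 11-8 prints the omitted 3500 µg rates directly below, the under-40% overdose limit and the unanimous vote for escalation are unaffected, and SAP 7.1 says the study is ending early. This limits the consequence to the accuracy of the record.

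**Conclusion.** The concern holds in all three parts.

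- Appendix 9 reports performance for a grid that shares two of nine levels with the current plan.
- Over-toxic MTD selection in the High scenario is understated by 3.7 points (18.3 printed, 22.0 correct) at 4 per cohort and by 4.7 points (19 printed, 23.7 correct) at 3 per cohort.
- The High and Mid average trial sizes exclude single-subject cohorts and are low by roughly 1 to 2 subjects.

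The first two results follow from the printed tables alone, given the column identification above. The third rests on Table 11-6 and on each simulated trial treating at least one subject at 6.5 µg. This is a fault in the reported performance, not a missing safeguard. It should be corrected because the appendix is the design's only performance evidence and the two wrong cells err in the favourable direction.

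**What to change.** Either of two routes would do.

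1. **Minimal, reasonable given the early termination.** Label Tables 11-4 to 11-8 as describing the previous dose grid, change the two High ≥33% cells to 22.0 and 23.7, and footnote that the average subject counts exclude single-subject cohorts. Do not add a constant to the averages, because the singles may also be absent from the model data and from the cap of 34.
2. **Fuller.** Re-run the simulation on the Table 6-2 levels and cohort sizes with every treated subject counted and modelled, and confirm or restate the prior for that grid. The 3500 µg reference may remain as a scaling constant.

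In both cases, reconcile the remaining single-subject text (protocol 6.2.1.1.1, Table 6-2 footnote a, SAP 3.1.1) with the 3 to 4 subjects shown in every row. If the switch has already happened because of the cohort 1 CRS events, say so.

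The first route costs a label, two cells, a footnote and text edits; the second adds a short simulation run. Neither changes data collection. The corrected High figures are less favourable than those printed.
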